Study Protocol

Title: Effects of Topical Bromfenac Solution on Macular Thickness in Cataract Patients Undergoing Phacoemulsification Surgery

Clinical Trial Registration Number: NCT06785090

Document Date: March 28, 2025.

1. Background and Rationale

Cystoid macular edema (CME) is a common postoperative complication following cataract surgery. Bromfenac, a topical nonsteroidal anti-inflammatory drug (NSAID), is hypothesized to reduce macular thickness and prevent CME. This study investigates the efficacy and safety of bromfenac in patients undergoing phacoemulsification.

2. Study Objectives

- **Primary Objective:** To assess the effect of bromfenac 0.09% ophthalmic solution on macular thickness after phacoemulsification.
- **Secondary Objective:** To evaluate potential adverse effects, including corneal erosion.

3. Study Design

- **Study Type:** Randomized controlled trial
- **Allocation:** Randomized
- **Intervention Model:** Parallel assignment
- **Masking:** Single-blinded (Investigator)

4. Eligibility Criteria

Inclusion Criteria:

1. All patients 18 years of age and older.
2. Patients diagnosed with cataracts.

Exclusion Criteria

- 1- Patients less than 18 years of age.
- 2- Patients with glaucoma, ocular hypertension, pseudo-exfoliation syndrome, or any optic nerve disease.
- 3- Patients with ocular diseases that might influence macular thickness, such as age-related macular degeneration, epiretinal membrane, history of uveitis, intraoperative complications, and traumatic cases.
- 4- Patients have undergone previous ocular surgery in the same eye, such as vitrectomy, intravitreal injection, retinal laser therapy, or corneal surgery
- 5- Patients who developed severe adverse effects from other drugs or had complications intraoperatively or postoperatively unrelated to bromfenac.
- 6- Patients take antiglaucoma medications.

- 7- Patients lost to follow-up.
- 8- Patients with an allergy to one of the postoperative medications.

5. Intervention and Follow-up

- **Group one-** consisted of forty-five patients who received 0.09% bromfenac ophthalmic solution twice daily in addition to Moxifloxacin 0.5% ophthalmic drops every 6hrs and Dexamethasone phosphate 0.1% ophthalmic drops every 4-6hrs.
- **Group two-** consisted of forty-two patients who received only Moxifloxacin 0.5% every 6hrs and Dexamethasone phosphate 0.1% ophthalmic drops every 4-6hrs without the administration of bromfenac 0.09% ophthalmic drops.

6. Outcome Measures

- **Primary Outcome:** Change in central macular thickness (CMT) measured by Optical Coherence Tomography (OCT)
- **Secondary Outcomes:** adverse effects

7. Statistical Methods

- Sample size calculation based on a power of 80% and significance level of 0.05.
- Independent t-test for intergroup comparisons.
- Paired t-test for intragroup pre- and post-treatment comparisons.

Statistical Analysis Plan (SAP)

1. Introduction

This SAP outlines the statistical methodologies for analyzing data collected in the clinical trial titled "Effects of Topical Bromfenac Solution on Macular Thickness in Cataract Patients Undergoing Phacoemulsification Surgery."

2. Study Population

- **Intent-to-Treat (ITT) Population:** All randomized patients.
- **Per-Protocol (PP) Population:** Patients who adhered to treatment and completed follow-up assessments.

3. Statistical Methods

- **Descriptive Analysis:** Means and standard deviations (SD) for continuous variables.
- **Inferential Analysis:**

- **Primary Outcome:** Two-sample t-test for between-group comparisons of CMT change.
- **Secondary Outcomes:**
 - Incidence of CME: Chi-square test.
 - Adverse effects: Fisher's exact test.

4. Handling of Missing Data

- **Missing data <5%:** Complete case analysis.
- **Missing data >5%:** Multiple imputation methods.

5. Software Used

All analyses will be performed using SPSS.

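### Exclusion 5 removes patients for postoperative complications unrelated to bromfenac, which conflicts with the SAP's ITT set, and nothing says which text governs the three planned tests

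*Combined protocol and SAP*

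**What the plan says.** Protocol section 4, exclusion 5, excludes "Patients who developed severe adverse effects from other drugs or had complications intraoperatively or postoperatively unrelated to bromfenac". Exclusion 3 also lists intraoperative events, in the phrase "history of uveitis, intraoperative complications, and traumatic cases".

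SAP section 2 defines two sets. ITT is "All randomized patients", with no exception. PP is "Patients who adhered to treatment and completed follow-up assessments".

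SAP section 3 plans a two-sample t-test for CMT change, a chi-square test for CME incidence and Fisher's exact test for adverse effects. None of the three is assigned to ITT or PP, and no primary analysis set is named. SAP section 4 deals with missing data but not with excluded patients.

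Four other statements bear on the point:

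- The secondary objective (protocol section 2) is "To evaluate potential adverse effects, including corneal erosion".
- Protocol section 1 says "Cystoid macular edema (CME) is a common postoperative complication following cataract surgery", and that bromfenac "is hypothesized to reduce macular thickness and prevent CME".
- Group two is treated "without the administration of bromfenac 0.09% ophthalmic drops" (protocol section 5).
- The groups are given as 45 and 42 patients. The text does not say whether these counts are before or after any exclusions, and it does not say when randomisation takes place.

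**The concern.** Exclusion 5 sits among the eligibility criteria but turns on events that follow surgery and study treatment. If it is applied, patients leave because of what happened after allocation, and the arms compared are no longer those that were randomised.

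The removal need not be balanced. Control patients receive no bromfenac, so none of their complications can be related to it and all meet the criterion. A bromfenac-arm complication meets it only if someone judges it unrelated. If a corneal erosion counts as a complication, a control erosion is removed and a bromfenac-arm erosion judged related is kept. That distorts the comparison named in the secondary objective.

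CME is a further exposure. The protocol calls it a postoperative complication, and item 5 does not exempt it. If it were covered, CMT would lose the part of any benefit that runs through CME. The CME test would lose its control events, or all its events if bromfenac-arm cases were removed too.

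If ITT prevails instead, item 5 has no effect on the analysis. A reader cannot tell which applies.

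**Working it through.** **1. The texts side by side.** Take a control patient who adheres to treatment, completes follow-up and has a postoperative complication.

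| Rule | Status |
|---|---|
| SAP ITT | in |
| SAP PP | in |
| Protocol exclusion 5 | out |

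Item 5 therefore matches neither set. Two softer readings cover only part of it. Reactions to other drugs could mean past history. Intraoperative events could precede allocation if randomisation followed surgery. Neither accounts for the postoperative clause.

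**2. The plan's own figure.** Protocol section 7 gives 80% power and a 0.05 level, but no difference or SD, so the sample size cannot be reproduced. Taking 45 and 42 as the group sizes, the detectable standardised difference (two-sided) is (1.960 + 0.842) × √(1/45 + 1/42) = 2.802 × 0.2145 = 0.60. The CMT illustrations use SD 20 µm and, where a benefit is assumed, 12 µm (12/20 = 0.6 SD). All SDs, rates, shifts and attribution shares below are assumptions, and 45 v 42 is taken as the count before removal.

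**3. Adverse effects (Fisher's exact test, two-sided 0.05; exact binomial enumeration).** Both arms have the same true rate and all control events are removed, so control always shows zero. Against 0/42, five bromfenac events in 45 give p = 0.056 and six give p = 0.027. The test therefore rejects when the bromfenac arm has six or more events: P(X ≥ 6) with n = 45 is 2.4% at a 5% rate and 29.2% at a 10% rate.

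| True rate in both arms | No removal (two-sided) | All bromfenac-arm events judged related | Half judged related |
|---|---|---|---|
| 5% | 1.0% | 2.4% | 0.09% |
| 10% | 2.6% | 29.2% | 2.4% |

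All rejections in the last two columns are against bromfenac.

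**4. CMT, complications other than CME (simulated pooled t-test).** Complications occur in 10% of each arm and add 0 or 30 µm, with no drug effect. If they are removed from control only, the expected spurious difference at 30 µm is 0.10 × 30 = +3 µm. False rejection over the 0 to 30 µm range is 5% if removed from both arms, 5 to 6% if half of bromfenac-arm events are judged related, and 5 to 9% if all are.

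**5. CMT, only if item 5 covers CME.** CME occurs in 2% of the bromfenac arm and 10% of control, and adds s = 50, 100 or 150 µm. Differences are bromfenac minus control. With no drug effect in non-CME eyes, the expected differences are:

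- no removal: (0.02 − 0.10) × s = −4, −8, −12 µm;
- removed from both arms: about 0;
- half of bromfenac-arm cases judged related: (0.01/0.99) × s ≈ +0.5, +1.0, +1.5 µm;
- removed from control only: 0.02 × s = +1, +2, +3 µm.

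Adding a 12 µm benefit in all bromfenac eyes, simulated power is:

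| Removal | s = 50 | s = 100 | s = 150 |
|---|---|---|---|
| None | 89.5% | 87.5% | 82.3% |
| Both arms | 76.3% | 76.4% | 76.2% |
| Half judged related | 71.2% | 63.6% | 56.6% |
| Control only | 66.4% | 52.5% | 41.6% |

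With equal CME rates, no drug effect and s of 50 to 150 µm, control-only removal gives CMT false rejection of 5 to 6% at 2% CME and 15 to 37% at 10%. With half judged related, the figures are 5% and 8 to 13%.

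**6. CME counts, under the same reading.** Suppose 1/45 v 6/42. Chi-square without correction is 87 × (1×36 − 44×6)² / (45 × 42 × 7 × 80) = 4.27, p = 0.039. Removing the six control cases leaves 1/45 v 0/36, p = 0.37, with the direction reversed.

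**The case against.** The other side has five fair points.

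- **Intent.** Because the SAP plans tests of CME and of adverse effects, the authors probably did not mean item 5 to delete those events. For CME this is persuasive, and steps 5 and 6 apply only if it is wrong. For adverse effects it is weaker: item 5 does not separate complications from adverse effects, although a control erosion is lost only if it is classed as a complication.
- **Masking.** The investigator is masked, and removal that follows the arm requires knowing the arm. A masked judgement could be less lopsided. But no section says who judges relatedness, so this does not rule the problem out.
- **Extreme inputs.** The 29% needs a 10% event rate, removal of every control event and attribution of every bromfenac-arm event. At half attribution, rejection is no higher than the two-sided rate without removal, though it all falls against bromfenac. This stands as a limit on the size, not on the contradiction.
- **Another reading.** Item 5 might end participation while ITT keeps the patient. That would be acceptable, but the documents do not say so.
- **Completeness.** Exclusion 7, for loss to follow-up, has the same conflict with ITT and would remove the patients for whom the missing-data rule exists. This is correct, and it belongs in the repair.

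**Conclusion.** The concern holds. The postoperative clause of exclusion 5 cannot act as an entry criterion, it fits neither SAP population, and no section resolves the conflict or assigns a population to any test. This is a rule that is wrong as written, not a missing detail, and confidence in that is high.

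The size of any bias is unknown. Under the assumptions shown, it runs from negligible (CMT false rejection of about 5% when complications are removed from both arms) to serious (29% false rejection on adverse effects; CMT power of 42 to 66% instead of 82 to 90% if CME is covered and removed from control only). The documents do not show that anyone was removed, and the 45 v 42 split is not evidence of it.

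**What to change.** - Confine exclusions 3 and 5 to facts known before randomisation, treat exclusion 7 the same way, and state when randomisation occurs.
- State in the SAP that the primary CMT, CME and adverse-effect analyses include all randomised patients by assigned arm, whatever the complication or its attributed cause, and that missing OCT data follow SAP section 4.
- Report any removed patients by arm and reason, and say whether 45 and 42 are counts before or after removal. Where removed patients have data, put them back.
- Keep any complication-free analysis as a sensitivity analysis only.

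Protocol section 5 describes the groups in the past tense, so treatment may already have been given. In that case the eligibility text should record what was actually done, and the all-randomised analysis and the table of removals carry the repair.

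The cost is wording in both parts of the document and one table. CMT variance may rise slightly because complicated eyes stay in, and there may be some missing OCT data to handle.

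### Loss to follow-up is listed as an exclusion criterion, which contradicts the SAP's ITT definition, and no population is named for the primary analysis

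*Combined protocol and SAP*

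**What the plan says.** Protocol section 4 lists "Patients lost to follow-up" as exclusion item 7. Two other exclusions can also rest on events during or after surgery. Item 5 excludes "Patients who developed severe adverse effects from other drugs or had complications intraoperatively or postoperatively unrelated to bromfenac", and item 3 includes "history of uveitis, intraoperative complications, and traumatic cases".

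SAP section 2 defines two populations:
- ITT: "All randomized patients"
- PP: "Patients who adhered to treatment and completed follow-up assessments"

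SAP section 3 gives the primary analysis as "Two-sample t-test for between-group comparisons of CMT change" and attaches no population to it. Protocol section 7 attaches none either. SAP section 4 uses complete cases when under 5% of data are missing and "Multiple imputation methods" when over 5% are missing.

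Protocol section 5 describes the groups by treatment received. Group one "consisted of forty-five patients who received 0.09% bromfenac ophthalmic solution twice daily", and group two is 42 patients given the other drops without bromfenac. The documents do not state the numbers randomised, the numbers lost, the time of randomisation, or the time of the OCT that defines CMT change.

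**The concern.** An eligibility criterion should be assessable before randomisation, and loss to follow-up is not. Used as an exclusion, it removes randomised patients because of something that happened later, which gives up the protection of randomisation. A result labelled ITT could then really be a completers' result, with the true loss hidden from the reader.

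If loss is related to the macular outcome, the between-group difference in CMT change is biased, and the direction is not known in advance. Losing control patients whose maculas thickened most would understate any benefit of bromfenac. Losing such patients from the bromfenac arm would overstate it.

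Item 5 adds an asymmetry where its events occur after randomisation. Control patients receive no bromfenac, so any complication of theirs is unrelated to it and leads to exclusion. A bromfenac patient whose complication is judged related stays in. Adverse effects are also a secondary outcome, so the safety counts are exposed as well.

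**Working it through.** **The texts side by side.** Take a patient who is randomised, treated, and never returns for OCT.

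| Text | Status of this patient |
|---|---|
| Protocol section 4, item 7 | Excluded |
| SAP section 2, ITT | Included |
| SAP section 2, PP | Not included (follow-up incomplete) |
| SAP section 4 | Counted as missing, but only if still in the analysis set |

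The first two rows cannot both hold, and no order of precedence is given. If item 7 governs, everyone who remains has completed follow-up. That set is completers; it is not the PP set, which also requires adherence.

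**When the 5% rule should act.** Inputs are the group sizes 45 and 42 (protocol section 5; 45 + 42 = 87) and the 5% threshold (SAP section 4). Let L be the number lost. There are two readings of the group sizes:
- Reading A: they are the numbers randomised, so share missing = L/N.
- Reading B: they are what remained after losses were removed, so share missing = L/(N + L).

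| Basis | L | Reading A | Reading B |
|---|---|---|---|
| Whole trial, N = 87 | 4 | 4/87 = 4.60% | 4/91 = 4.40% |
| Whole trial, N = 87 | 5 | 5/87 = 5.75% | 5/92 = 5.43% |
| Bromfenac arm, N = 45 | 2 | 2/45 = 4.44% | 2/47 = 4.26% |
| Bromfenac arm, N = 45 | 3 | 3/45 = 6.67% | 3/48 = 6.25% |
| Control arm, N = 42 | 2 | 2/42 = 4.76% | 2/44 = 4.55% |
| Control arm, N = 42 | 3 | 3/42 = 7.14% | 3/45 = 6.67% |

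The trigger is 5 losses over the whole trial, or 3 in one arm, under both readings. The SAP does not say which basis applies. With item 7 applied, the numerator from loss is 0, so its contribution is 0% on either basis. A missing or unusable scan in a retained patient would still count.

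**Scale of a possible bias (all inputs assumed).** If a fraction f of one arm is dropped, and those lost differ from completers in mean CMT change by g SD, that arm's mean shifts by f × g SD. Equal f and g in both arms would cancel in the difference, so the illustration puts all the loss in one arm.

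| f | g = 0.5 | g = 1 |
|---|---|---|
| 5% | 0.025 SD | 0.05 SD |
| 10% | 0.05 SD | 0.10 SD |
| 20% | 0.10 SD | 0.20 SD |

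For comparison, the difference detectable with 45 and 42 patients at 80% power and 0.05 (two-sided assumed) is (1.960 + 0.842) × √(1/45 + 1/42) = 2.802 × 0.2145 = 0.60 SD. The noncentral t gives 0.61 SD. The illustrated biases therefore run from 0.025/0.61 = 4% to 0.20/0.61 = 33% of that difference.

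**The case against.** The strongest reply is that the SAP is the text that defines analysis sets. It defines ITT without exceptions, keeps completers in a separate set, and has a missing-data rule that only makes sense if patients without outcomes stay in. On that reading item 7 is a misplaced withdrawal rule that does no harm, and no document reports that anyone was lost or removed. This is a fair reading, and it limits what can be claimed: the inconsistency is certain, whereas a biased result is conditional on item 7 being used. It does not resolve the conflict, because no precedence is stated. Even on that reading the primary test has no assigned population.

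Three narrower points also have weight:
- The threshold counts show when imputation is due. They do not measure distortion of the treatment difference.
- Under reading B, the whole-trial trigger of 5 assumes that items 3 and 5 removed no one else. If k further randomised patients with measured outcomes were removed, the share is 5/(92 + k). At k = 8 this is 5/100 = 5.0%, which neither branch of the rule covers.
- If randomisation follows surgery, intraoperative complications are legitimate exclusions before randomisation. Items 3 and 5 conflict with ITT only where the events come after it, and the documents do not give the timing.

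**Conclusion.** The concern holds, and this must be fixed. Item 7 contradicts the ITT definition, and the population for the primary comparison is not named. Followed as written, item 7 turns the primary result into a completers' comparison and keeps loss to follow-up from ever triggering imputation, although 5 losses over the trial or 3 in one arm should do so. Those counts rest on 45 and 42 being either the numbers randomised or the numbers left after losses alone were removed.

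The bias itself cannot be sized or signed from the documents. Under the assumed inputs above it is small at 5% loss and not negligible at 20%. The need for correction does not depend on a large bias, because the conflict decides who enters the primary analysis.

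**What to change.** 1. Delete item 7 from the eligibility criteria.
2. State when randomisation takes place, and reconcile items 3 and 5 with ITT so that events after randomisation do not remove anyone from the ITT set.
3. Name ITT, analysed as randomised, as the primary population, and PP as a sensitivity analysis.
4. Report numbers randomised, lost and analysed per arm, and say what 45 and 42 represent.
5. State the OCT time point for CMT change, so that a missing primary outcome can be identified.
6. Count missing primary outcomes over all randomised patients, say whether 5% applies to the whole trial or per arm, and cover exactly 5%.
7. Specify that the imputation model includes arm and baseline CMT. Because imputation assumes data are missing at random, a delta-shift sensitivity analysis is advisable; it is an addition and not essential to the correction.

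The cost is protocol and SAP wording and a little more analysis. Part of the protocol is in the past tense, so recruitment may have ended. If so, randomisation records must be retrieved to identify any patients who were removed and return them to the ITT set.

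### Does the lack of a stated OCT time point for the primary outcome call for a change to the plan?

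*Combined protocol and SAP*

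**What the plan says.** The primary objective in protocol section 2 is "To assess the effect of bromfenac 0.09% ophthalmic solution on macular thickness after phacoemulsification", which places the effect after surgery but not at any particular time. Protocol section 6 gives the primary outcome as "Change in central macular thickness (CMT) measured by Optical Coherence Tomography (OCT". SAP section 3 analyses it with a "Two-sample t-test for between-group comparisons of CMT change". The nearest thing to timing is in protocol section 7: "Paired t-test for intragroup pre- and post-treatment comparisons".

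Section 5 has follow-up in its title. For the first group it says that it "consisted of forty-five patients who received 0.09% bromfenac ophthalmic solution twice daily" alongside the antibiotic and steroid drops, and it describes a second group of forty-two without bromfenac. It gives no treatment length, visit list or OCT day.

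Two other items depend on a schedule. SAP section 3 lists "Incidence of CME: Chi-square test", and SAP section 2 defines the per-protocol set as "Patients who adhered to treatment and completed follow-up assessments".

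**The concern.** A primary outcome normally carries a time. Macular thickness can change over the weeks after surgery, so a difference in change is fully interpretable only when its time is known. Without a time, three things could go wrong:

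- The result could not be placed on a post-operative time scale or compared with another study.
- If scan days varied between patients, the estimate would average effects at different times and might lose power.
- If several post-operative scans existed and the most favourable were called primary, the false-positive rate would exceed 5%.

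The schedule is also what would give CME incidence its counting period and the per-protocol set its list of required assessments.

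**Working it through.** **Inputs.** Group sizes of 45 and 42 come from protocol section 5. The 80% power and 0.05 level come from protocol section 7, "Sample size calculation based on a power of 80% and significance level of 0.05". I take the test as two-sided. Scan counts, correlations and timing patterns are not in the documents; where used below they are assumptions.

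**The plan's own figure.** The 80% power cannot be reproduced, because no effect size or SD is given. It can only be inverted:

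- Normal approximation: (1.960 + 0.842) × √(1/45 + 1/42) = 2.802 × 0.2145 = 0.60 SD of CMT change.
- Noncentral t with 85 degrees of freedom: 0.608 SD.

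This standardised figure is the same whichever day the scan is taken, so it does not measure the gap.

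**What the text describes.** Taken together, the passages give one change score, one between-arm t-test on it, and one paired test of values before and after treatment. That is a baseline scan and a follow-up scan. The only plural is in the per-protocol definition, where the assessments may include adverse-effect checks as well as OCT. With one post-operative scan per patient there is nothing to choose among, the missing-data percentage is well defined, and the false-positive rate is 5% if timing does not differ by arm. Nothing in the documents suggests that it does.

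**If scan days varied (assumption).** Let p be the share of scans at another time and f the fraction of the effect seen then. The average effect is multiplied by 1 − p(1 − f). Starting from 0.608 SD and ignoring the small added variance:

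| p | f | multiplier | power |
|---|---|---|---|
| 0 | – | 1 | 80% |
| 0.25 | 0.5 | 1 − 0.25 × 0.5 = 0.875 | 68.8% |
| 0.50 | 0.5 | 1 − 0.50 × 0.5 = 0.75 | 55.6% |
| 0.50 | 0 | 1 − 0.50 × 1 = 0.50 | 28.8% |

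The sign of this effect is also assumed. With no intended day on record, an off-time effect could equally be larger: f = 1.5 and p = 0.25 give a multiplier of 1 + 0.25 × 0.5 = 1.125, and power above 80%.

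**If several scans were taken and any significant one were called primary (assumption).** The chance of at least one |z| > 1.96 under no effect is:

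| scans | correlation 0.5 | correlation 0.7 | correlation 0.9 |
|---|---|---|---|
| 1 | 5.0% | 5.0% | 5.0% |
| 2 | 9.1% | 8.4% | 7.0% |
| 3 | 12.5% | 10.9% | 8.4% |
| 4 | 15.6% | 13.0% | 9.4% |

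Only the first row matches the plan as written. The others need extra scans and a selection rule that appear nowhere in it.

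**What a change would do.** The documents give no basis for naming a day, so an amendment could only ask the sponsor to record when the scans are taken. The t-test, its population and the missing-data rule would stay the same.

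**The case for a change.** The best case for acting is that this single file is both protocol and SAP, so no other document supplied here holds the schedule, and a primary outcome without a time is incomplete. Nothing at these points looks redacted or lost in conversion. The plural in the per-protocol definition leaves room for more than one visit, the documents do not rule out more than one OCT, and stating the visit would cost a few sentences.

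The omission stands, and so does the loss of interpretability for someone who has only these pages. The step to a statistical defect does not stand. That the documents do not exclude several scans is not evidence that several were taken or that one would be selected.

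The two dependent items add little. CME incidence is not among the secondary outcomes in protocol section 6, and its counting period is a smaller, separate matter. The per-protocol set is not assigned to the primary analysis. A written schedule could alter who belongs to that set, but not who belongs to the intent-to-treat set.

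Section 5 is in the past tense, so 45 and 42 may be achieved counts. A time written in now might then only describe what was done.

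**Conclusion.** No change to the plan follows. This is a gap in description that the investigators can fill sensibly: they know when the post-operative OCT is done, and a report of the trial would state it. The demonstrated effect on the false-positive rate, bias and power is nil. The calculable losses (power of 69%, 56% or 29%; false-positive rates of 7.0% to 15.6%) belong to scenarios the documents do not describe.

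The conclusion rests on two assumptions: one post-operative OCT per patient, which is the plain reading of protocol section 7 and SAP section 3, and scan timing that does not differ by arm. It would need another look if more than one post-operative OCT existed and no dated record, made before data by arm were seen, fixed the primary one. In that case the choice of visit would be post hoc. With a single scan no choice is made, and that label would be wrong.

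### Do the within-arm paired t-tests in protocol section 7 undermine the conclusion about bromfenac?

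*Combined protocol and SAP*

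**What the plan says.** The primary objective in protocol section 2 is "To assess the effect of bromfenac 0.09% ophthalmic solution on macular thickness after phacoemulsification". Protocol section 7 names two tests, one after the other: "Independent t-test for intergroup comparisons" and "Paired t-test for intragroup pre- and post-treatment comparisons". It does not say which of them supports the objective, and it does not call the paired test descriptive.

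Section 3 of the SAP, under inferential analysis, gives the primary outcome one test: "Two-sample t-test for between-group comparisons of CMT change". The paired test appears nowhere in the SAP.

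Protocol section 5 puts 45 patients in the bromfenac group and 42 in the control group. Both groups have phacoemulsification and receive the same antibiotic and steroid drops, so bromfenac is the only planned difference.

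**The concern.** The effect of bromfenac is a between-arm question. A pre-to-post change within an arm mixes the effects of surgery, dexamethasone, time and any drug effect, and only the randomized contrast separates the last of these from the rest. A paired test can therefore be significant in the bromfenac arm although bromfenac does nothing. It is also a familiar mistake to set the two paired p-values side by side and treat significance in one arm but not the other as evidence that the arms differ.

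Section 7 gives the paired tests no stated role, so it could be read as opening a second route to a positive conclusion on the primary outcome, one that does not hold the 5% error rate. If the report took that route, a chance pattern could be presented as efficacy.

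**Working it through.** **Inputs from the documents.** Arm sizes are 45 and 42 (protocol section 5). Power is 80% and the significance level is 0.05 (protocol section 7). Sidedness is not stated, so I take the tests as two-sided.

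**Assumptions.** The documents give no CMT mean, SD or target difference. I assume normally distributed changes, the same SD in both arms, and the same true mean change *d* in both arms, in SDs of the change. Equal *d* means no bromfenac effect. I vary *d* from 0 to 0.8.

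**1. The plan's own figure.** The 80% power cannot be reproduced without an effect size. Solving backwards for the between-arm test gives the standardized difference detectable with these arms:

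(1.960 + 0.842) × √(1/45 + 1/42) = 2.802 × 0.2145 = 0.601 (0.608 with the t distribution).

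This describes the between-arm test only. Nothing in the documents ties the sample size to the paired tests.

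**2. How often each paired test is significant.** In an arm of size *n*, the paired statistic follows a noncentral t with *n* − 1 degrees of freedom and noncentrality *d*√*n*. At *d* = 0.3 the noncentrality is 0.3 × √45 = 2.012 for bromfenac and 0.3 × √42 = 1.944 for control. The probabilities of significance are 50.3% and 47.6%.

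**3. How often the arms disagree.** The arms are independent. With *a* and *b* the probabilities for bromfenac and control:

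- bromfenac only: *a*(1 − *b*)
- control only: *b*(1 − *a*)
- exactly one: the sum of the two

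At *d* = 0.3: 0.503 × 0.524 = 0.264; 0.476 × 0.497 = 0.237 (0.236 before rounding the inputs); sum 0.500.

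| Common change (SD) | Bromfenac significant | Control significant | Bromfenac only | Control only | Exactly one |
|---|---|---|---|---|---|
| 0 | 5.0% | 5.0% | 4.8% | 4.8% | 9.5% |
| 0.2 | 25.9% | 24.4% | 19.6% | 18.1% | 37.7% |
| 0.3 | 50.3% | 47.6% | 26.4% | 23.6% | 50.0% |
| 0.4 | 74.7% | 71.6% | 21.2% | 18.1% | 39.3% |
| 0.5 | 90.7% | 88.6% | 10.4% | 8.3% | 18.6% |
| 0.6 | 97.6% | 96.7% | 3.2% | 2.3% | 5.6% |
| 0.8 | 99.9% | 99.9% | 0.1% | 0.1% | 0.1% |

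**4. Direction.** The last column counts patterns for and against bromfenac. If thickness falls in both arms, bromfenac only is the pattern that would look favourable. If it rises in both, control only would look like protection. Either is about half of the last column, with peaks near 26% and 24% at 0.3 SD.

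**5. The test the SAP uses.** In the between-arm difference the common change cancels, so its error rate does not depend on *d*. In 100,000 simulated trials each at *d* = 0, 0.3 and 0.5, it rejected in 4.95%, 4.95% and 4.87%. The same simulations gave exactly one significant arm in 9.4%, 50.4% and 18.7%, in agreement with the table.

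**6. What replacing the tests would do.** A 95% confidence interval for an arm's mean change excludes zero exactly when the paired p-value is below 0.05. Reporting intervals instead of p-values would give readers the same information about each arm, and they could misread it in the same way. The between-arm estimate, interval and p-value would not change.

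**The case for a change.** The case for a change is that section 7 does not call the paired tests descriptive, the protocol and SAP do not list the same tests, and no sentence bars a reader from comparing the two within-arm p-values. A single line of wording would close the matter at no cost in patients, visits or data. A large common change does not make the tests safe either: at 0.5 SD the bromfenac-arm test alone is significant in 90.7% of trials with no drug effect.

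The facts in this stand. The protocol and SAP do differ, and a within-arm p-value says nothing about bromfenac. What does not stand is the step to an inflated error rate for this plan. Each paired test holds 5% for the question it asks, which is whether thickness changed in that arm. The percentages in the table belong to a rule under which one significant arm counts as efficacy, and neither document states or implies that rule. The claim that nothing says which test serves the objective fails once the SAP is read with the protocol, because the SAP names that test.

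**Conclusion.** The concern is right as a statistical principle but does not call for a change to the plan. An analyst who follows the documents draws the conclusion on bromfenac from the two-sample t-test of CMT change, whose error rate stays at about 5% whatever change the arms share. The paired tests remain a by-product that describes each arm.

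The misreading that they could invite would occur, in the favourable direction, in anything from 0.1% to about 26% of trials with no drug effect. Where in that range depends on a common change that the documents do not let us place. It would also take an inference that the plan does not make. A label on the within-arm results would be tidy, but it would alter neither the primary result nor its validity. The omission is one that analysts fill sensibly from the SAP.

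This rests on two-sided testing, normally distributed changes with equal SD in both arms, and reporting that keeps to the SAP's primary analysis.
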